Trial monitoring will be done by a safety monitoring committee, which includes the PI, primary mentor ([name]) a statistician ([name]) and an expert in the care of older adults ([name]). We will evaluate the progress of the study on a monthly basis, including periodic assessments of data quality (safety and integrity) and timeliness, recruitment, accrual and retention, participant risk versus benefit, and other factors that can affect study outcome; consider factors external to the study when relevant information becomes available, such as scientific or therapeutic developments that may have an impact on the safety of the participants or the ethics of the trial; review study performance; and discuss the resolution of problems. Furthermore, we will monitor adverse events (AEs), including serious adverse events (SAEs) and unanticipated problems (UPs). An Adverse Event is any untoward medical occurrence in a patient or clinical investigation participant and which does not necessarily have a causal relationship with this treatment. Participants will be queried regarding any changes in their health and medications at each contact. The informed consent document will list the daytime and after hours contact information for the site Principal Investigator. All AE and SAE reporting will be done in adherence with IRB guidelines; the PI will notify the IRB within 48 hours of any serious possible or potentially study-related AEs. The report will include the description of the AEs and any actions taken by the PI. SAEs in this population include, but are not limited to death, hospitalization, evidence of abuse, suicidal ideation, and medical emergencies. The PI will also keep a log of all AEs. Any deviations related to the protocol will be reported to the IRB using a deviation form immediately upon the discovery of the deviation. Given the non-invasive nature of the intervention, the team does not anticipate AEs beyond the average rate of these events in this population. The literature in the field will be continually appraised by the team. If any team member uncovers new information that would impact the safety of the participants or the ethics of our study, the PI and entire mentoring team will discuss the issues. At this time, given the low risk of the intervention, there is no plan for interim analyses or any stopping rules.

The following documents are currently attached to this item:

There are no documents attached for this item.

Risk / Benefit Assessment

We believe that the benefits far outweigh the risks to participants in this study. We feel this study is minimal risk.

General Attachments

The following documents are currently attached to this item:

There are no documents attached for this item.

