
Characteristics of the Study Population

Target population

Older adults with insomnia and mild cognitive impairment

Subjects enrolled by Penn Researchers

40

Subjects enrolled by Collaborating Researchers

0

Accrual

ACCESS TO THE POPULATION We plan to recruit 27 participants from three sources: 1) Division of Geriatric Medicine Division Ralston House clinic: There are currently 2,864 active patients, with 40% having mild cognitive impairment (MCI), yielding a potential 1,145 patients with MCI. We will use EPIC to generate a list of eligible participants coming in for clinic visits each week. Staff will introduce patients to the study team for further screening. This first method of recruitment is on hold due to Covid-19. 2) PennSeek search of MCI and insomnia yielded 870 potential participants. After obtaining permission to contact from their provider and completing a telephone screening call, consent and research visits will be set up via telephone or video-conferencing call. 3) Recruitment will also include contacting participants from a recruitment database (I.e., subject registry), which contains names of over 1000 individuals who participated in or were not eligible for study team members' previous or on-going studies and have indicated a willingness to be contacted for future studies. Participant information will be accessed via REDCap, and participants will be contacted by phone to determine interest and eligibility for this study. **ANALYSIS:** Power calculation was done using PASS v21. We initially planned to power the study on two primary outcomes, sleep latency and health related quality of life and required a sample size of 40. However, given that this is a pilot study, Covid-19 and other time constraints, we decided to power the study on our main primary outcome of sleep latency. Thus, the study is powered to detect time averaged difference of two groups in a repeated measures design for the primary, continuous outcome of sleep latency using the generalized estimating equation (GEE) approach. To estimate the necessary sample size, we assumed equal allocation between the treatment and control groups. The minimum time averaged difference in sleep latency between the two groups we were interested in detecting was set at 4.5 minutes with a standard deviation of 4. We expect an even larger effect size, given the work of Cassidy-Eagle et al.⁴² Assuming a baseline correlation $r = 0.80$ between multiple observations from the same subject over time and anticipating 20% attrition, we require 27 total participants in the study to achieve 80% power.

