
The following documents are currently attached to this item:

There are no documents attached for this item.

Deception

Does your project use deception? Deception could be considered any direct misinformation presented to the subject or omission of key information pertaining to the design or nature of the project.

No

International Research

Are you conducting research outside of the United States?

No

Analysis Plan

Power Analysis for Sample Size described previously under "Accrual". Descriptive statistics will be used to characterize the sample, with measures of central tendency and variation for continuous measures, and frequencies and percentages for dichotomous and categorical variables. Descriptive estimates will be generated for all participants at each of the observed time points, and by intervention group within each time point. Distributional assumptions and outliers will be assessed via graphical approaches. Baseline characteristics between groups will be compared appropriate two sample -test or non-parametric Wilcoxon Rank Sum test for continuous variables and Chi-square test for categorical variables. Primary analysis will be carried out under the intent to treat (ITT) framework. To evaluate the difference between groups in our primary outcome, we will utilize the GEE model with time, group, and group by time as the primary predictors. A simple exchangeable correlation structure will be used to model the correlation between multiple observations from the same subject. Given that GEE is less likely to suffer from model convergence, we changed our initial approach from mixed-model to GEE. GEE analysis does not require complete data over time and all available data from all subjects will be used in estimation. We have assumed 20% missingness in our sample size estimation. For missingness more than 20% we will explore imputing missing values when feasible. Given the real time data transmission and ability to call participants and remind them to complete sleep diary, we do not anticipate a great deal of missing data. We will report end of study effect sizes along with p-values and parameter estimates. We will construct reference cell contrasts to evaluate change relative to baseline

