and consecutive time comparisons will be conducted by profile contrasts. It is reasonable to assume due to our sample size GEE models may fail to converge. In such situations we will obtain difference in score between two time points and conduct two sample t-test or Wilcoxon Rank Sum test for two groups comparisons. We will adjust our type I error rate to adjust for multiple comparison under this scenario.

The following documents are currently attached to this item:

There are no documents attached for this item.

Data confidentiality

Paper-based records will be kept in a secure location and only be accessible to personnel involved in the study.

- x Computer-based files will only be made available to personnel involved in the study through the use of access privileges and passwords.**
- x Prior to access to any study-related information, personnel will be required to sign statements agreeing to protect the security and confidentiality of identifiable information.**
- x Wherever feasible, identifiers will be removed from study-related information.**

A Certificate of Confidentiality will be obtained, because the research could place the subject at risk of criminal or civil liability or cause damage to the subject's financial standing, employability, or liability.

A waiver of documentation of consent is being requested, because the only link between the subject and the study would be the consent document and the primary risk is a breach of confidentiality. (This is not an option for FDA-regulated research.)

- x Precautions are in place to ensure the data is secure by using passwords and encryption, because the research involves web-based surveys.**

Audio and/or video recordings will be transcribed and then destroyed to eliminate audible identification of subjects.

Subject Confidentiality

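### N = 27 rests on 80% power for a time-averaged difference in sleep latency, but the analysis plan does not list that contrast and names no primary one

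*Combined protocol and SAP*

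**What the plan says.** The Accrual section (text headed ANALYSIS) says that "the study is powered to detect time averaged difference of two groups in a repeated measures design". The outcome is sleep latency and the method is GEE. The smallest time-averaged difference of interest is 4.5 minutes, with SD 4, within-person correlation 0.80 and 20% attrition, giving 27 participants for 80% power. Alpha, sidedness, the number of occasions and the role of baseline are not stated.

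The Analysis Plan refers back to that section ("Power Analysis for Sample Size described previously under" Accrual) and then says "we will utilize the GEE model with time, group, and group by time as the primary predictors", with an exchangeable correlation. The comparisons it goes on to list are:

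- at the last visit: "We will report end of study effect sizes along with p-values and parameter estimates"
- for change, within the GEE: "We will construct reference cell contrasts to evaluate change relative to baseline"
- from one visit to the next: "consecutive time comparisons will be conducted by profile contrasts"
- if the GEE does not converge, "we will obtain difference in score between two time points and conduct two sample t-test", or a rank-sum test, with "We will adjust our type I error rate to adjust for multiple comparison under this scenario"

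None is called primary, and a time average is not in the list. Overall objectives asks for both immediate (one month) and sustained (three months) efficacy without ranking them. Primary outcome variable(s) gives three measurement times for sleep latency: baseline, 4 weeks and 16 weeks.

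**The concern.** A sample-size statement means something only for the test it was computed for. Here the powered quantity and the listed comparisons are different functions of the same repeated measurements. Their variances differ, and so does their power.

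Because the GEE contrasts evaluate change from baseline, baseline must be one of the outcome time points. A time average taken from that model therefore needs a decision on whether baseline is in it, and the plan does not make that decision. Treatment cannot affect the baseline visit.

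Without a named primary contrast, any of several results could later be read as the main one. The plan promises a type I error adjustment only for the fallback tests, so a choice among the GEE contrasts would be uncontrolled. That matters for a pilot that will report p-values and is meant to inform larger trials.

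**Working it through.** **Inputs.** From Accrual: difference 4.5 min, SD 4 (variance 16), r = 0.80, attrition 20%, N = 27, power 80%. Assumed: two-sided alpha 0.05, equal variance at every visit and exchangeable correlation. Completers: 27 × 0.8 = 21.6, so n = 10.8 to 11 per arm.

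**Step 1: reproduce N.** For an average over m occasions, n per arm = 2(1.960 + 0.842)² × 16 × [1 + (m − 1)0.8]/m ÷ 4.5². The total divided by 0.8 is:

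- m = 2: 27.9, so 28
- m = 3: 10.75 per arm, 21.5/0.8 = 26.9, so 27
- m = 4: 26.4, so 27
- m = 5: 26.05, so 27

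The stated 27 reproduces with three occasions, but four or five fit as well. The figure does not reveal how many occasions were used or whether baseline was one.

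**Step 2: power of each contrast.** Power = Φ(δ/SE − 1.96), with SE = √(2V/n) and V the variance per person. Here δ = 4.5 is taken as the effect at each follow-up visit. This is a translation, because Accrual defines 4.5 as the time average.

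| Contrast (r = 0.80) | V | In the Analysis Plan list? | Normal, n = 10.8–11 | t, 11 per arm |
|---|---|---|---|---|
| Average of three occasions, 4.5 min | 16 × 2.6/3 = 13.87 | No | 80–81% | 77% |
| Average of weeks 4 and 16, unadjusted | 16 × 1.8/2 = 14.4 | No | 79% | 75% |
| End-of-study difference, unadjusted | 16 | Yes, adjustment not specified | 74–75% | 71% |
| Single-visit change from baseline | 32 × 0.2 = 6.4 | Yes | 98–99% | 98% |
| Week 4 to week 16, effect maintained (δ = 0) | 6.4 | Yes | 5% | 5% |

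Example, end of study with n = 11: SE = √(32/11) = 1.706; 4.5/1.706 − 1.96 = 0.678; power 0.751. Change, n = 11: SE = √(12.8/11) = 1.079; 4.5/1.079 − 1.96 = 2.21; power 0.987.

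**Step 3: dependence on r.** The documents give only r = 0.80; lower values are a sensitivity range. At r = 0.5 the change variance is 32 × 0.5 = 16, the same as a single visit, so power is about 75%. The change contrast falls below 80% when r is under about 0.56. For the fallback t-test at an illustrative adjusted alpha of 0.025, power is 95%, 59% and 44% at r = 0.8, 0.5 and 0.3.

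**Step 4: dependence on what 4.5 minutes means.** Suppose the three averaged occasions were the three scheduled visits, baseline included.

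- If the effect is 4.5 min at each follow-up, the average is (0 + 4.5 + 4.5)/3 = 3.0 min. With V = 13.87, power is 46–47%.
- If the three-visit average is 4.5 min, the follow-up effect is 4.5 × 3/2 = 6.75 min. With n = 11, 6.75/1.706 − 1.96 = 2.00, so end-of-study power is about 97–98%.

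**Step 5: a baseline-adjusted contrast.** V = 16(1 − r²) for one visit and 16[(1 + r)/2 − r²] for the average of two follow-ups, with 4.5 min at each.

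| Contrast | r = 0.8 | r = 0.5 | r = 0.3 |
|---|---|---|---|
| Week 4, normal | 99% | 85–86% | 78–79% |
| Week 4, simulated ANCOVA with t reference, 11 per arm | 98% | 80% | 72% |
| Weeks 4 and 16 averaged, normal | over 99% | 96% | 94% |
| Weeks 4 and 16 averaged, simulated as above | over 99% | 93% | 90% |

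**The case against.** The best defence is that the powered quantity is stated, only not repeated. Accrual names a time-averaged difference estimated by GEE, the Analysis Plan refers back to that section and uses a GEE, and group is among the main predictors. The baseline-free version, the average of weeks 4 and 16, can be estimated from that model with 79% power, close to the claimed 80%. Much of this stands: the sections do not conflict outright, and the gap could be closed with little text.

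It does not remove the point. With group, time and their interaction in the model and baseline as the reference cell, the group coefficient is the arm difference at baseline, not a time average. The average has to be specified, including which visits enter, and the plan instead lists other comparisons.

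It is also fair that the spread of power depends on reading 4.5 minutes as a per-visit effect, and that an unadjusted end-of-study test is only one reading of the reporting sentence. Both are conditions on the figures above.

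A reader might infer that true power is only 46–47%. The documents do not support that. It requires both that baseline was averaged, which is not stated, and that the effect is 4.5 minutes at each follow-up. Reading 4.5 minutes as the three-visit average gives about 97–98% at end of study.

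**Conclusion.** The stated 80% reproduces for a time-averaged difference but is not the power of any comparison in the Analysis Plan, and no comparison is named primary. Taking 4.5 minutes at each follow-up, SD 4, r = 0.80, two-sided alpha 0.05 (not stated in the plan) and about 11 completers per arm, the listed between-arm comparisons lie on either side of 80%: 74–75% unadjusted at end of study and 98–99% for change. The latter drops to about 75% at r = 0.5.

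It may be tempting to conclude that the trial is underpowered or that 27 is wrong. Neither follows: the change contrast exceeds 80% at the plan's r, and the baseline-free time average is within about a point of it. Confidence is high on the missing ranking and lower on the size of the power spread. This should be fixed, but it is a matter of specification, not a flaw in the trial's size.

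**What to change.** **Analysis Plan.** Before analysis, name one primary contrast: the between-arm difference in post-baseline diary sleep latency, adjusted for baseline latency. The sponsor chooses week 4 or the average of weeks 4 and 16, and labels every other comparison secondary. The mismatch alone could be closed by naming the time average and saying whether baseline is in it. Adjustment is preferable because it keeps baseline out of the outcome, uses data already collected, and has at least the power of the change contrast (week 4 at r = 0.5: 85–86% against about 75%).

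**Accrual.** State alpha, sidedness and the number of occasions. Restate power at N = 27 for the chosen contrast over a range of r, for example 0.3 to 0.8, preferably with a t reference. Any power quoted for the fallback should use the adjusted type I error.

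**Cost.** One sentence, one recalculation, and one extra fitted model if the change contrasts are kept as secondary, since they need the GEE now in the plan. The restated power will differ from 80%. Current Status of Study shows enrolment closed at 27, so no participants or data are added and N stays as it is.

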Convened Board Increase in target enrollment for investigator initiated research or potential Phase I research Expanding inclusion or removing exclusion criteria where the new population may be at increased risk Revised risk information with active participants Minor risk revisions that may affect a subject's willingness to continue to participate Expedited Review Increase in target enrollment at Penn where overall enrollment target is not exceeded or potentially sponsored research Expanding inclusion or removing exclusion where the new population has the same expected risk as the previous, based on similarities of condition Revised risk information with subjects in long-term follow-up Minor risk revisions with no subjects enrolled to date Expedited Review

Modification Summary

Please describe any required modification to the protocol. If you are using this form to submit an exception or report a deviation, enter 'N/A' in the box below.

We initially planned to power the study on two primary outcomes, sleep latency and health related quality of life and required a sample size of 40. However, given that this is a pilot study, Covid-19 and other time constraints, we decided to power the study on our main primary outcome of sleep latency. Our new sample size requirement is 27. We would like to change our analysis plan. For continuous outcomes, both mixed-effects model and GEE approach provide population average estimates. Even though we proposed to use mixed-effects models with random slopes and random intercepts in our original proposal, we feel that we may run into issues with model convergence and model estimation especially for model with random slope due to smaller sample size. Since GEE with exchangeable covariance matrix is less likely to suffer from model convergence issue, we decided to change from mixed-model to GEE. The estimates from mixed-model with only random-intercept and GEE with exchangeable covariance matrix should be very similar and both of these models. For categorical outcomes, since mixed-model provides subject level estimate and GEE provides population averaged estimates changing from one to another would be answering two different questions. But our outcome is continuous and both approaches will provide population averaged estimate, using either mixed-effects model or GEE is appropriate.

Risk / Benefit

Does this amendment alter the Risk/Benefit profile of the study?

No

Change in Consent

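### The plan makes no small-sample provision for GEE inference on 27 participants; an uncorrected robust Wald test at nominal 5% would reject a true null about 7-8% of the time for single contrasts

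*Combined protocol and SAP*

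**What the plan says.** The Modification Summary explains the move from a mixed model to GEE by the reduced sample size: with the mixed model, "we may run into issues with model convergence and model estimation especially for model with random slope due to smaller sample size". It says nothing about whether GEE tests are valid at that size.

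Under Accrual, "the study is powered to detect time averaged difference of two groups in a repeated measures design", and "we require 27 total participants in the study to achieve 80% power".

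The Analysis Plan then gives the model: "To evaluate the difference between groups in our primary outcome, we will utilize the GEE model with time, group, and group by time". It adds an exchangeable working correlation and use of all available data. On reporting it says: "We will report end of study effect sizes along with p-values and parameter estimates".

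The one provision tied to sample size comes at the end of the Analysis Plan: "It is reasonable to assume due to our sample size GEE models may fail to converge". It continues: "In such situations we will obtain difference in score between two time points and conduct two sample t-test or Wilcoxon Rank Sum test". A type I error adjustment for multiple comparisons is promised under that scenario only.

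No section says whether the GEE standard errors are model-based, robust or bias-corrected, whether tests are Wald or score, which reference distribution is used, or what alpha is.

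**The concern.** The sandwich variance used with GEE is justified for a large number of independent clusters. Here the clusters are participants, and there are 27. Two errors act in the same direction. The uncorrected sandwich is built from fitted residuals and is biased downward, and a normal cut-off takes no account of the variance having been estimated on about 25 degrees of freedom. Both make p-values too small.

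The plan's fallback does not help. A t-test on difference scores handles small samples properly, but it is reserved for non-convergence. A GEE with a saturated group-by-time mean and a continuous outcome has little reason not to converge, so the analysis that will almost certainly be run is the unprotected one. With the estimator unstated, it could also be chosen after the data are seen.

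What is at stake is the calibration of the reported p-values, and of any intervals, for immediate and sustained efficacy, which the Abstract says will inform larger trials.

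**Working it through.** **Inputs from the documents.** N = 27, difference 4.5 minutes, SD 4, correlation 0.80, 20% attrition, equal allocation, 80% power (Accrual); simple 1:1 randomisation (Method for Assigning Subjects to Groups); baseline, 4 and 16 weeks (Primary outcome variable(s)); exchangeable GEE with time, group and their interaction (Analysis Plan).

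**Assumed.** Two-sided 5%, since no alpha is stated. Dropout at random, half before week 4 and half before week 16. Where used: correlation 0.5, a decaying correlation (0.8 between adjacent visits, 0.64 from baseline to week 16), and a lognormal outcome.

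**1. The plan's sample size.** For the mean of T visits the variance is 4² × (1 + (T-1) × 0.8)/T. With T = 3 this is 16 × 2.6/3 = 13.87. Total N = 4 × 13.87 × (1.960 + 0.842)²/4.5² = 21.5, and 21.5/0.8 = 26.9, so 27. The plan's figure reproduces with three time points and a normal approximation (T = 2 gives 27.9).

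**2. Closed form, complete data, 13.5 per arm.** With complete data the saturated GEE reduces to cell means whose robust variance divides by n instead of n-1. The uncorrected standard error is therefore too small by a factor √(12.5/13.5) = 0.962, and the statistic should be referred to t on 25 df.

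- Both causes: P(|t₂₅| > 1.96 × 0.962) = P(|t₂₅| > 1.886) = 7.1%
- Normal cut-off alone: P(|t₂₅| > 1.96) = 6.1%
- Small standard error alone: P(|Z| > 1.886) = 5.9%
- Joint 2-df group-by-time test, both causes: 9.0%

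**3. Full GEE simulation under the null.** N = 27, 20,000 trials in each of seven settings: (a) r = 0.8, complete, 14/13; (b) r = 0.8, 20% dropout, 14/13; (c) as (b) with simple randomisation; (d) r = 0.5, dropout, simple randomisation; (e) decaying correlation, complete; (f) decaying correlation, dropout, simple randomisation; (g) lognormal, r = 0.8, dropout, simple randomisation.

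| Method | Single contrasts | Joint 2-df test |
|---|---|---|
| Uncorrected sandwich, normal or chi-square | 6.9-7.9% | 9.1-10.7% |
| Uncorrected sandwich, t(N-2) | 5.7-6.8% | not computed |
| Kauermann-Carroll, t(N-2) or F(2,N-2) | 4.6-5.5% | 5.1-6.6% |
| Mancl-DeRouen, t(N-2) or F(2,N-2) | 3.7-4.5% | 3.8-5.2% |

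The 6.9-7.9% applies both to the week-4 and week-16 interaction contrasts and to the time-averaged difference. The ratio of mean standard error (root mean square) to true SD was 0.945-0.972, that is, 3-6% too small. Non-convergence: 0 of 7 × 20,000 = 140,000 fits. The plan's fallback t-test on change to week 16 rejected 5.0%.

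**4. Cross-checks.** A separately coded simulation, 20,000 trials per scenario, with 22 or 27 participants, fixed or simple randomisation, with and without dropout, normal and lognormal outcomes, gave 6.7-8.1% for single contrasts and 9.1-10.5% for the joint test. A standard package's GEE with robust z (2,500 runs, r = 0.8, dropout, simple randomisation) gave 7.9% at week 16 and 8.6% for the time-averaged follow-up, with Monte Carlo error of about 1.1 points and no failures to converge.

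**5. Model-based standard errors.** With a normal reference and a truly exchangeable correlation of 0.8, single contrasts reject 5.5-7.6%. Under the assumed decaying correlation, week 16 rejects 11.2-11.8% and week 4 rejects 3.4-4.1%.

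**6. Power for 4.5 minutes averaged over the two follow-ups, 27 randomised, 20% dropout.** Uncorrected 85.6%; Kauermann-Carroll with t 81.2%; Mancl-DeRouen with t 78.6%.

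**The case against.** The strongest objection is that the 7-8% describes a choice the plan does not make. It never says robust, Wald, normal reference or 5%. What is documented is the silence, and the consequence depends on the estimator eventually used. That is right, and the claim is conditional for that reason. But the alternative the plan leaves open is not safe: model-based standard errors are also anti-conservative under the plan's own correlation. The 11-12% at week 16 does rest on an assumed decay, and week 4 is conservative in the same setting.

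Second, the excess is 2-3 percentage points in a pilot with no stopping rules, and nothing in the documents turns on p < 0.05. This stands as a limit on seriousness. It does not make the p-values correct, and the plan promises to report them.

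Third, the plan promises neither confidence intervals nor a joint interaction test. Both points are true. The coverage and width figures matter only if intervals are reported, and the 9.1-10.7% only if a joint test is run.

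Fourth, the choice among corrections is partly preference. Mancl-DeRouen with a normal reference also came out near nominal, at 4.8-5.6%. With a t reference its power is 78.6%, slightly under the 80% target.

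Fifth, the power figures cover one contrast, averaged over two follow-ups, whereas the plan's N reproduces with three time points. For change from baseline, the SD is 4 × √(2 × 0.2) = 2.53, and power for 4.5 minutes exceeds 98% even after 20% loss. The power cost of correction is therefore contrast-specific and would be smaller there.

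**Conclusion.** The concern holds. The plan adopts GEE because the sample is small but gives no small-sample rule for the GEE tests, and its fallback is tied to an event that should almost never occur. If the uncorrected robust Wald test is used at nominal two-sided 5%, single contrasts reject a true null about 7-8% of the time, so a reported p of 0.05 is really about 0.07-0.08. Any joint 2-df test would be at about 9-11%.

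This rests on the plan's N, SD, correlation and attrition, and on an assumed two-sided 5% and dropout at random. It changed little across the other correlations, arm imbalance and skewness tried. Point estimates are not affected. The effect is modest, but the plan should be changed before analysis.

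**What to change.** Add to the Analysis Plan:

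- the primary contrast and a two-sided alpha;
- for single GEE contrasts, a Kauermann-Carroll bias-corrected sandwich variance with a t reference on N-2 degrees of freedom (Mancl-DeRouen with t is a more conservative option);
- for any joint 2-df group-by-time test, Mancl-DeRouen with F(2, N-2), because Kauermann-Carroll with F still reaches 5.1-6.6%.

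Model-based exchangeable standard errors should not be the remedy: the visits are unequally spaced, and the week-16 test is badly inflated if correlation decays.

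The cost is a short addition to the text and a software setting; the documents do not name the analysis package, so its availability should be confirmed. No new data are needed. Week-16 confidence intervals widen by about 10% (Kauermann-Carroll) or 16% (Mancl-DeRouen). For the 4.5-minute difference averaged over follow-up, the power given up is 85.6 - 81.2 = 4.4 points or 85.6 - 78.6 = 7.0 points, part of which was never real because it came from the inflated error rate.
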